### 7.3 Rationale for Dose Selection

[REDACTED]

[REDACTED]

[REDACTED]

[REDACTED]

[REDACTED]

[REDACTED]

[REDACTED]

[REDACTED]

## 8 STUDY OBJECTIVES

The overall objective is to evaluate the safety and efficacy of teprotumumab in the treatment of TED in subjects who participated in the lead-in study (HZNP-TEP-301) and who were either proptosis non-responders at Week 24 of HZNP-TEP-301 or were proptosis responders at Week 24 but meet the criteria for re-treatment due to relapse (see [Section 9.3.4](#)) during the Follow-Up Period of HZNP-TEP-301.

### 8.1 Primary Objective

The primary objective is to evaluate the effect of teprotumumab on the proptosis responder rate (i.e., the percentage of subjects with a  $\geq 2$  mm reduction from Baseline in the study eye without deterioration [ $\geq 2$  mm increase] of proptosis in the fellow eye) at Week 24.

### 8.2 Secondary Objectives

Secondary objectives will evaluate the effect of teprotumumab on the following:

1. Percentage of subjects with a Clinical Activity Score (CAS) value of 0 or 1 at Week 24 in the study eye.
2. Mean change from Baseline to Week 24 in proptosis measurement in the study eye.
3. Diplopia responder rate (i.e., the percentage of subjects with baseline diplopia  $> 0$  in study eye who have a reduction of  $\geq 1$  grade with no corresponding deterioration [ $\geq 1$  grade worsening] in the fellow eye) at Week 24.
4. Mean change from Baseline to Week 24 in the Graves' Ophthalmopathy Quality of Life (GO-QoL) questionnaire overall score.

### 8.3 Exploratory Objectives

Exploratory objectives will evaluate the effect of teprotumumab on the following:

1. The overall responder rate (percentage of subjects with  $\geq 2$ -point reduction in CAS **AND**  $\geq 2$  mm reduction in proptosis from Baseline, provided there is no corresponding deterioration [ $\geq 2$  point/mm increase] in CAS or proptosis in the fellow eye) at Week 24.
2. Clinical Measures of Severity individual response status frequencies and percentage of responders for each component of clinical severity at Week 24.
3. Mean change from Baseline to Week 24 in the CAS.
4. Overall responder rate at Week 24 stratified by the level of response (high responders, responders, low responders, and non-responders; see [Section 9.6.3.2.1](#) for definitions).
5. Mean change from Baseline to Week 24 in the GO-QoL questionnaire visual functioning (VF) and appearance (A) subscale scores.
6. Mean change from Baseline to Week 24 on the motility component of the Clinical Measures of Severity.

7. Evaluate pharmacokinetic (PK) parameters of teprotumumab to estimate exposure and understand PK-PD relationships.

## 9 INVESTIGATIONAL PLAN

### 9.1 Overall Study Design and Plan

This study will be conducted at up to 16 sites in the United States and Europe.

This is a multi-center, open-label extension study of HZNP-TEP-301 examining the safety and efficacy of teprotumumab in the treatment of TED in adult subjects. Subjects who complete the 24-week double-masked Treatment Period in Study HZNP-TEP-301 and are proptosis non-responders or were proptosis responders at Week 24 but meet the criteria for re-treatment due to relapse (see [Section 9.3.4](#)) during the Follow-Up Period of HZNP-TEP-301 will be eligible for enrollment. The study treatment previously administered in HZNP-TEP-301 (teprotumumab or placebo) will remain masked throughout this extension study.

All subjects who choose to participate will receive 8 infusions of teprotumumab (10 mg/kg for the first infusion followed by 20 mg/kg for the remaining 7 infusions) in an open-label fashion. The Baseline (Day 1) Visit of this extension study will occur within 14 days after the final visit of Study HZNP-TEP-301 (Week 24 for proptosis non-responders and up to Week 72 for subjects who relapse). During the open-label Treatment Period, study drug infusions are scheduled for Day 1 (Baseline), and Weeks 3, 6, 9, 12, 15, 18, and 21 (with a final visit at Week 24 of the 24-Week Treatment Period).

All study drug dosing will be performed at the clinic under the supervision of clinic staff, and at any scheduled infusion, the infusion rate may be reduced or the dose may be interrupted or held based on decreased tolerability (see [Section 9.4.6.3.2](#) for details). On each dosing day, scheduled assessments (except for adverse event [AE] and concomitant medication use monitoring, which will be monitored throughout the clinic visit) will be completed prior to study drug dosing. After each of the first 2 infusions, subjects will be contacted by phone/email the following day and will return to the clinic 1 week after the infusion (Weeks 1 and 4) for safety and tolerability assessments; additional phone/email contacts and clinic visits may also be conducted for any subject experiencing an infusion-associated event.

[figure not shown]
After completion of the Treatment Period, subjects who were proptosis non-responders in Study HZNP-TEP-301 will enter a 24-week Follow-Up Period, during which study drug will not be administered and clinic visits are scheduled for 1, 3, and 6 months (visit months 7, 9, and 12) after the Week 24 Visit; if any of these subjects discontinue from the Follow-Up Period prior to the Month 12 Visit, they will return to the clinic and undergo the scheduled Month 12 assessments prior to study discharge. Those who complete the Month 12 Visit will be contacted 6 and 12 months later via phone or email by research staff to enquire if any treatment for TED has been received since last study contact. If yes, subject will be questioned regarding type of treatment and outcome/response.

Subjects who relapsed during the Follow-Up Period of HZNP-TEP-301 and choose to enter this extension study will not participate in the Follow-Up Period. For these subjects, the last clinic visit is at Week 24. Those who complete the Week 24 Visit will be contacted 6 and 12 months later via phone or email by research staff to enquire if any treatment for TED has been received since last study contact. If yes, subject will be questioned regarding type of treatment and outcome/response.

[figure not shown]
An overview of the study design is presented in [Figure 9.1](#), and details of study activities were previously presented in [Section 2.1, Schedule of Assessments](#).

## Figure 9.1 Schematic of Study Design

### Subjects who were proptosis non-responders in Study HZNP-TEP-301

### Subjects who relapsed in Study HZNP-TEP-301

\* Infusion of study drug. M=Month; W=Week.

1. Teprotumumab 20 mg/kg (10 mg/kg on Day 1 followed by 20 mg/kg q3W for the remaining 7 infusions).
2. Visit windows are  $\pm$  1 day for Weeks 1 and 4,  $\pm$  3 days for Weeks 3, 6, 9, 12, 15, 18, and 21, and  $\pm$  7 days for Week 24.
3. Visit windows of  $\pm$  7 days.
4. Proptosis non-responders from Study HZNP-TEP-301 who complete the Month 12 Visit and subjects who relapsed during the Follow-Up Period of HZNP-TEP-301 and complete the Week 24 Visit.
5. Visit must occur within 14 days after the final visit of HZNP-TEP-301.
6. Subjects will be contacted by phone/email the day following the first and second infusions for safety and tolerability assessments; phone/email contacts will also occur the day after any clinic visit where a subject experiences an infusion-related AE.
7. If a subject wishes to discontinue dosing, the subject will return to the clinic and undergo the scheduled Week 24 assessments.
8. If a subject participates in the Follow-Up Period and prematurely discontinues prior to Month 12, he/she will return to the clinic and undergo the Month 12 assessments prior to study discharge.

## 9.2 Discussion of Study Design

The study population consists of subjects who participated in the lead-in study (HZNP-TEP-301) and who were either proptosis non-responders at Week 24 of HZNP-TEP-301 or were proptosis responders at Week 24 but meet the criteria for re-treatment due to relapse (see [Section 9.3.4](#)) during the Follow-Up Period of HZNP-TEP-301. The study population enrolled in HZNP-TEP-301 was well-defined and consistent with the expected target population for whom teprotumumab will be indicated (adult subjects with active moderate-to-severe TED).

The measurements used in this study for the primary and secondary endpoints (proptosis, CAS, and GO-QoL questionnaire) are established and well-validated endpoints that have been shown to correlate significantly with TED.

In order to maintain the study mask in HZNP-TEP-301, all subjects in this open-label extension study will undergo the same dosing regimen of teprotumumab (10 mg/kg on Day 1 followed by 20 mg/kg q3W for the remaining 7 infusions), regardless if they received teprotumumab or placebo in HZNP-TEP-301.

Given the teratogenic effects of teprotumumab noted in a monkey embryo-fetal development toxicity study (see [Section 7.1.3.2](#) for details) and PK profile of teprotumumab (see [Section 7.1.3.4.3](#)), all subjects (men and women) are required to use adequate contraception and report any pregnancies for at least 6 months after the last dose of study drug. Six months after the last dose, the estimated plasma concentration (0.2 µg/mL) is considered reasonably safe with a low risk of teratogenicity. Furthermore, a 6-month waiting period is in line with recommendations given for other teratogens, such as cytostatic chemotherapy.

## 9.3 Selection of Study Population

### 9.3.1 Inclusion Criteria

Eligible subjects must meet **all** of the following criteria:

1. Written informed consent.
2. Completed the 24-week double-masked Treatment Period in Study HZNP-TEP-301.
3. Proptosis non-responder (< 2 mm reduction in proptosis in the study eye) at Week 24 of Study HZNP-TEP-301 OR proptosis responder at Week 24 who relapses (see [Section 9.3.4](#)) during the Follow-Up Period of Study HZNP-TEP-301.
4. Subject must be euthyroid with the baseline disease under control, or have mild hypo- or hyperthyroidism (defined as free thyroxine [FT4] and free triiodothyronine [FT3] levels < 50% above or below the normal limits) at the most recent clinic visit. Every effort should be made to correct the mild hypo- or hyperthyroidism promptly and to maintain the euthyroid state for the full duration of the clinical trial.
5. Alanine aminotransferase (ALT) or aspartate aminotransferase (AST)  $\leq 3$  times the upper limit of normal (ULN) or serum creatinine <1.5 times the ULN (according to age) at the most recent clinic visit.
6. Diabetic subjects must have well-controlled disease (defined as HbA1c < 9.0% at most recent clinic visit).
7. Does not require immediate surgical ophthalmological intervention and is not planning corrective surgery/irradiation during the course of the study.
8. Women of childbearing potential must have a negative urine pregnancy test at Baseline/Day 1. Subjects who are sexually active with a non-vasectomized male partner must agree to use 2 reliable forms of contraception during the trial and continue for 180 days after the last dose of study drug. One of the 2 forms of contraception is

recommended to be hormonal, such as an oral contraceptive. Hormonal contraception must be in use for at least one full cycle prior to Baseline. Highly effective contraceptive methods (with a failure rate less than 1% per year), when used consistently and correctly, includes implants, injectables, combined oral contraceptives, some intrauterine devices (IUDs), sexual abstinence or vasectomized partner.

9. Male subjects must be surgically sterile or, if sexually active with a female partner of childbearing potential, must agree to use a barrier contraceptive method from Baseline through 180 days after the last dose of study drug.
10. Subject is willing and able to comply with the prescribed treatment protocol and evaluations for the duration of the study.
11. Has not received any treatment for TED since Week 24 of the HZNP-TEP-301 study.

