**Inclusion Criteria (continued):**

5. Alanine aminotransferase (ALT) or aspartate aminotransferase (AST)  $\leq 3$  times the upper limit of normal (ULN) or serum creatinine  $< 1.5$  times the ULN (according to age) at the most recent clinic visit.
6. Diabetic subjects must have well-controlled disease (defined as HbA1c  $< 9.0\%$  at most recent clinic visit).
7. Does not require immediate surgical ophthalmological intervention and is not planning corrective surgery/irradiation during the course of the study.
8. Women of childbearing potential must have a negative urine pregnancy test at Baseline/Day 1. Subjects who are sexually active with a non-vasectomized male partner must agree to use 2 reliable forms of contraception during the trial and continue for 180 days after the last dose of study drug. One of the 2 forms of contraception is recommended to be hormonal, such as an oral contraceptive. Hormonal contraception must be in use for at least one full cycle prior to Baseline. Highly effective contraceptive methods (with a failure rate less than 1% per year), when used consistently and correctly, includes implants, injectables, combined oral contraceptives, some intrauterine devices (IUDs), sexual abstinence or vasectomized partner.
9. Male subjects must be surgically sterile or, if sexually active with a female partner of childbearing potential, must agree to use a barrier contraceptive method from Baseline through 180 days after the last dose of study drug.
10. Subject is willing and able to comply with the prescribed treatment protocol and evaluations for the duration of the study.
11. Has not received any treatment for TED since Week 24 of the HZNP-TEP-301 study.

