14. Ophthalmic exam: best corrected visual acuity, pupil exam, color vision assessment, Ishihara color plates (or equivalent) or related red desaturation, intraocular pressure, and slit lamp exam. If significant abnormalities are noted compared to previous visits, including a loss of 2 lines or more of vision, development of pupil abnormalities including APD, rise in intraocular pressure, development of corneal infiltrates or other abnormalities not here specified but of concern to the ophthalmologist, further investigations of visual function will be conducted according to the ophthalmologist decision.
15. Vital signs (heart rate, blood pressure, respiratory rate, temperature) will be measured at all clinic visits. Vital signs will be measured pre- and post-infusion on Day 1 and Week 3, and pre-dose on all other infusion days. Additional vital signs will be monitored if infusion-associated AEs occur (see [Section 9.5.4.3](#) for details).
16. Non-diabetic subjects should be fasting at Weeks 1 and 4 only. Diabetic subjects should be fasting at each visit blood glucose is evaluated.
17. ALT/AST must be  $\leq 3$  x the upper limit of normal (ULN) and serum creatinine must be  $< 1.5$  x the ULN (according to age) at the most recent clinic visit to be eligible for enrollment.
18. Subjects must be euthyroid with the baseline disease under control or have mild hypo- or hyperthyroidism (defined as free thyroxine [FT4] and free triiodothyronine [FT3] levels < 50% above or below the normal limits) at the most recent clinic visit. Every effort should be made to correct the mild hypo- or hyperthyroidism promptly and to maintain the euthyroid state for the full duration of the clinical trial.
19. HbA1c must be < 9.0% at the most recent clinic visit. If the HbA1c is elevated and considered clinically significant at any time point after Baseline, it will be repeated approximately every 45 days until it returns to normal or the baseline value.
20. If a sample is positive in the ADA test, after confirmatory and reactive titer testing, the sample will then be tested for NAb. If the subject tests positive for NAb, he/she will be followed until levels either revert to Baseline or the subject's value decreases or remains stable. Any subject with a positive NAb test at Week 48 (or PW) during the Follow-Up Period will continue to be followed until the subject's value decreases or remains stable.

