**Table 9.4 Schedule of Clinical Laboratory Safety Tests, Including Thyroid Panel and Hyperglycemia Monitoring**

Analysis Panel	Treatment Period											Follow-Up Period		
	Base-line 	W1	W3	W4 M1	W6	W9	W12 M3	W15	W18	W21	W24 M6	W28 M7	W36 M9	W48 M12
Chemistry (excl. glucose)	X 		X		X	X	X		X		X		X	X
Thyroid (FT3, FT4, TSH) 	X		X		X	X	X		X		X		X	X
Hematology	X	X	X	X	X	X	X	X	X	X			X	X
Glucose 	X	X	X	X	X	X	X	X	X	X			X	X
HbA1c	X 						X				X		X	X
Urinalysis	X		X		X	X	X		X		X		X	X
Urine pregnancy 	X		X		X	X	X	X	X	X	X	X	X	X

FT3=free triiodothyronine; FT4=free thyroxine; HbA1c=glycated hemoglobin; M=Month; TSH=thyroid stimulating hormone; W=Week.

1. If Day 1 (Baseline) of the extension study occurs on the same day as the final visit of HZNP-TEP-301, assessments do not need to be repeated, and the final assessments from the lead-in study will serve as the Baseline assessments for the extension study.
2. ALT/AST must be  $\leq 3$  x the ULN and serum creatinine must be  $< 1.5$  x the ULN (according to age) at most recent clinic visit for enrollment.
3. Subjects must be euthyroid with the baseline disease under control or have mild hypo- or hyperthyroidism (defined as FT4 and FT3 levels  $< 50\%$  above or below the normal limits) at the most recent clinic visit. Every effort should be made to correct the mild hypo- or hyperthyroidism promptly and to maintain the euthyroid state for the full duration of the clinical trial.
4. Non-diabetic subjects will fast at Weeks 1 and 4 only. Diabetic subjects will fast for each blood glucose evaluation. NOTE: Subjects with severe hyperglycemia that does not abate to mild or moderate intensity with anti-diabetic treatment (dose may be skipped up to 2 times prior to permanently discontinuing study drug, see [Section 9.4.6.3.2](#) for details) will be permanently discontinued from study drug.
5. HbA1c must be  $< 9.0\%$  at most recent clinic visit for enrollment. If the HbA1c is elevated and considered clinically significant at any time point after Baseline, it will be repeated approximately every 45 days until it returns to normal or baseline value.
6. Perform for female subjects of childbearing potential (including those with an onset of menopause  $< 2$  years prior to Screening of HZNP-TEP-301, non-therapy-induced amenorrhea for  $< 12$  months prior to Screening of HZNP-TEP-301, or not surgically sterile [absence of ovaries and/or uterus]).

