##### **9.5.6.1 Day 1/Baseline**

The Baseline (Day 1) Visit must occur within 14 days of the final visit of HZNP-TEP-301. If Day 1 of the extension study occurs on the same day as the final visit of HZNP-TEP-301 and an assessment is scheduled for both visits, assessments do not need to be repeated, and the final assessments from the lead-in study will serve as the Baseline assessments for the extension study.

Potential study subjects will be informed fully regarding the nature of the study and possible AEs, and will receive a copy of the ICF for review. Potential study subjects must read the ICF and sign the document after the Investigator has answered all questions to the study candidate's satisfaction. Further procedures can begin only after the ICF has been signed. The original signed ICF will be retained by the Investigator and a copy will be given to the study subject.

Study candidates will be evaluated for study entry according to the stated inclusion and exclusion criteria ([Section 9.3](#)). The Investigator will evaluate the results of all examinations, including

clinical laboratory tests, from the most recent clinic visit and will determine each candidate's suitability for the study. The Investigator must review these results before determining that a candidate is eligible for study drug treatment. The Baseline urine pregnancy test performed for all female candidates of childbearing potential must be negative in order for subjects to be eligible for treatment. The following procedures will be performed at Baseline to establish each candidate's general health and eligibility for enrollment into the study:

- Obtain signed, written informed consent and permission to use Protected Health Information (in accordance with the Health Insurance Portability and Accountability Act [HIPAA]). Refusal to provide this permission excludes an individual from eligibility for study participation. Record date informed consent was given and who conducted the process on the appropriate source documentation.
- Determine study eligibility through review of the inclusion/exclusion criteria (see [Section 9.3](#))
- Obtain predose blood samples for hematology and chemistry (including thyroid, glucose, and HbA1c) analysis (see [Section 9.5.4.6](#) for details concerning test results and study participation).
- Collect predose blood samples for immunogenicity and PK testing.

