10.8. CLINICAL LABORATORY SAFETY EVALUATIONS

With the exception of urine pregnancy tests, a central study laboratory will be used for all protocol-specified clinical laboratory parameters. [Table 3](#) provides the schedule of collection.

Table 3 Schedule of Clinical Laboratory Safety Tests, Including Thyroid Panel and Hyperglycemia Monitoring

Analysis Panel	Treatment Period											Follow-Up Period		
	BL ¹	W1	W3	W4 M1	W6	W9	W12 M3	W15	W18	W21	W24 M6	W28 M7	W36 M9	W48 M12
Chemistry (excl. glucose)	X ²		X		X	X	X		X		X		X	X
Thyroid (FT3, FT4, TSH) ³	X		X		X	X	X		X		X		X	X
Hematology	X	X	X	X	X	X	X	X	X	X	X		X	X
Glucose ⁴	X	X	X	X	X	X	X	X	X	X	X		X	X
HbA1C	X ⁵						X				X		X	X
Urinalysis	X		X		X	X	X		X		X		X	X
Urine pregnancy ⁶	X		X		X	X	X	X	X	X	X	X	X	X

BL=Baseline; FT3=free triiodothyronine; FT4=free thyroxine; HbA1C=glycated hemoglobin A1C; M=Month; SCR=Screening; TSH=thyroid stimulating hormone; W=Week.

1. If Day 1 (Baseline) of the extension study occurs on the same day as the final visit of HZNP-TEP-301, assessments do not need to be repeated, and the final assessments from the lead-in study will serve as the Baseline assessments for the extension study.
2. ALT /AST must be ≤ 3 x the ULN and serum creatinine must be < 1.5 x the ULN (according to age) at most recent clinic visit for enrollment.
3. Subjects must be euthyroid with the baseline disease under control or have mild hypo- or hyperthyroidism (defined as FT4 and FT3 levels < 50% above or below the normal limits) at the most recent clinic visit. Every effort should be made to correct the mild hypo- or hyperthyroidism promptly and to maintain the euthyroid state for the full duration of the clinical trial.
4. Non-diabetic subjects will fast at Weeks 1 and 4 only. Diabetic subjects will fast for each blood glucose evaluation. NOTE: Subjects with severe hyperglycemia that does not abate to mild or moderate intensity with anti-diabetic treatment (dose may be skipped up to 2 times prior to permanently discontinuing study drug, see Section 9.4.6.3.2 for details) will be permanently discontinued from study drug.
5. HbA1C must be < 9.0% at most recent clinic visit for enrollment. If the HbA1C is elevated and considered clinically significant at any time point after Baseline, it will be repeated approximately every 45 days until it returns to normal or baseline value.

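### Inclusion criterion 5 joins the liver and creatinine limits with *or*, while four footnotes in the protocol and SAP require both for enrolment

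*Protocol*

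**What the plan says.** Criterion 5 appears twice in the current protocol, with *or* each time.

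- **Section 9.3.1, item 5:** ALT or AST at or below 3 "times the upper limit of normal (ULN) or serum creatinine <1.5 times the ULN (according to age) at the most recent clinic visit".
- **Synopsis, Inclusion Criteria, item 5:** the same rule, again with "times the upper limit of normal (ULN) or serum creatinine".

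The list opens with "Eligible subjects must meet all of the following criteria". That joins the numbered items to each other but does not alter the *or* inside item 5.

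Four footnotes state the same limits with *and*.

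- **Protocol Section 2.1, footnote 17:** ALT/AST no more than 3 × "the upper limit of normal (ULN) and serum creatinine must be" below 1.5 × ULN, as a condition of eligibility.
- **Protocol Table 9.4, footnote 2:** "the ULN and serum creatinine must be" below 1.5 × ULN, as a condition of enrolment.
- **SAP Table 1, footnote 17:** matches the Section 2.1 footnote.
- **SAP Table 3 (Section 10.8), footnote 2:** "the ULN and serum creatinine must be < 1.5 x the ULN (according to age) at most recent clinic visit for enrollment".

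Protocol Section 9.5.6.1 (Day 1) sends site staff to both versions. Entry is judged by Section 9.3: "Study candidates will be evaluated for study entry according to the stated inclusion and exclusion criteria". The blood-sampling step refers to Section 9.5.4.6, which leads to Table 9.4, "for details concerning test results and study participation".

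**The concern.** The limits are there to keep subjects with marked liver or renal abnormality from being dosed. With *or*, criterion 5 fails only when ALT, AST and creatinine are all outside their limits. A subject with normal transaminases and creatinine well above 1.5 × ULN meets it, as does a subject with normal creatinine and both transaminases above 3 × ULN. The footnotes bar both.

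A site working from the criterion text alone could enrol someone the footnotes exclude, and two sites could decide differently on identical results. Reporting is exposed too. The listing of criteria not met (SAP Listing 16.2.3.2) and the major-deviation summaries (SAP Section 7.5) could classify the same subject differently according to the wording applied.

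**Working it through.** The plan states no figure to reproduce, and the sample size has no statistical basis (Protocol Section 9.6.4). The check compares the texts and enumerates the logic.

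**Statements in current text.** *Or*: 2 (Synopsis; Section 9.3.1). *And*: 4 (Protocol Section 2.1 footnote 17; Protocol Table 9.4 footnote 2; SAP Table 1 footnote 17; SAP Table 3 footnote 2). The marked-up schedule in the protocol's Summary of Changes is not counted.

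**Rules compared.** Let A, S and C mean that ALT, AST and creatinine are within their limits.

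- Criterion 5, literal: A or S or C.
- Footnotes, ALT/AST meaning both enzymes: A and S and C.
- Footnotes, ALT/AST meaning either enzyme: (A or S) and C.

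The documents do not define ALT/AST, so both footnote readings are carried.

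| ALT | AST | Creatinine | Criterion 5 | Footnotes, both | Footnotes, either |
|---|---|---|---|---|---|
| in | in | in | admit | admit | admit |
| in | in | out | admit | bar | bar |
| in | out | in | admit | bar | admit |
| out | in | in | admit | bar | admit |
| in | out | out | admit | bar | bar |
| out | in | out | admit | bar | bar |
| out | out | in | admit | bar | bar |
| out | out | out | bar | bar | bar |
| **Admitted of 2³ = 8** | | | **7** | **1** | **3** |

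**Disagreements.**

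- Footnotes read as both enzymes: 7 − 1 = 6.
- Footnotes read as either enzyme: 7 − 3 = 4. Three have creatinine outside its limit with at least one enzyme within; one has creatinine within and both enzymes outside.

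**Sensitivity to the reading of criterion 5.** If the enzyme pair means both throughout, criterion 5 becomes (A and S) or C and admits 5 patterns, against 1 for the footnotes: 5 − 1 = 4 disagreements.

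**Common to all readings.** Two patterns always disagree: both enzymes within and creatinine outside; and both enzymes outside and creatinine within.

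**Direction.** No pattern is admitted by the footnotes and refused by criterion 5 under any reading.

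**The case against.** The strongest reply is that the protocol, taken whole, gives one answer. Inclusion criteria are necessary conditions, and the footnotes add a further mandatory one, so a subject who passes criterion 5 but fails the footnotes is not eligible. The strict version also sits where staff look on Day 1, and the investigator must review the laboratory results before declaring eligibility. Exclusion 1 (Section 9.3.2) allows refusal on grounds of risk. The lead-in study's exclusion criteria carry over as well. Two of the four footnotes are in the SAP, which governs analysis and not enrolment, so within the protocol the count is two against two. The pattern counts carry no weights, and no estimate changes.

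Much of this stands. A site that applies every provision reaches the stricter rule, the intent was very probably *and*, and the counts describe logic, not subjects.

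It does not rescue the criterion. Section 9.5.6.1 directs the eligibility decision to Section 9.3, where the loose text sits, and no provision ranks that text against the footnotes. The precedence given to the SAP in Protocol Section 9.6 concerns analyses. Exclusion 1 is discretionary and sets no liver or creatinine limit. The lead-in criteria are not reproduced in these documents, so nobody can show from them that the gap is closed.

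**Conclusion.** The inconsistency is real, and criterion 5 is wrong as written. On the literal reading it passes 7 of 8 patterns where the footnotes pass 1 or 3. That leaves 6 or 4 in conflict, or 4 if the enzyme pair means both throughout. The exact count rests on the undefined meaning of ALT/AST; the existence and direction of the conflict do not.

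The patterns are not equally likely, and the documents give no way to estimate how many subjects fall in the disputed ones. The documents also give no evidence that anyone was wrongly enrolled.

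The effect is confined to entry safety and the classification of eligibility deviations. The ITT population is all enrolled subjects and serves both efficacy and safety (SAP Section 5.1), so no analysis population or efficacy estimate changes. It should be fixed because it is a safety rule, but it does not threaten the trial's conclusions.

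**What to change.** 1. In the Protocol Synopsis and Section 9.3.1, reword item 5 to require ALT and AST each at or below 3 × ULN, and serum creatinine below 1.5 × ULN for age, at the most recent clinic visit.
2. In the four footnotes, replace ALT/AST with ALT and AST, so that the enzyme rule also has one meaning.
3. Check once each enrolled subject's entry values, from the visit the rule refers to, against the joint rule. List any subject who fails it as an eligibility deviation.

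The cost is a change of connectives in two places, a matching clarification in four footnotes, and one review of laboratory data already collected. Design, analysis populations and estimates stay as they are.
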